#### 6.2.4 Assay Run Data

Any Printouts corresponding to assay runs will be maintained and a copy placed in a study binder. A record will be maintained regarding assay reagents and calibrators by lot number and expiration date.

#### 6.2.5 Discordant Results

If any discordant results are generated during the clinical study, further testing using a second high-sensitivity EUA PCR method, CDC's Influenza SARS-CoV-2 (Flu SC2) Multiplex Assay performed by Premier Laboratories, will be performed with specimens yielding discordant results obtained with the initial PCR methodology. If the NP swab sample has been retained and stored properly, and there is sufficient sample available, the same sample will be run on the second PCR assay. Both the AN specimen and the nasopharyngeal swab specimen can be repeat tested if possible. The results from the discrepant analysis will be reported as a footnote in the performance table. The discordancy will not be used to alter the performance data.

#### **6.3 Data Analysis**

#### 6.3.1 Acceptance Criteria for Method Comparison

The study sponsor or designee will ensure that all specimens are analyzed appropriately, and results are accurately transcribed to an excel spreadsheet for analysis. Qualitative results from the Antigen Test and quantitative results from the PCR Test may be evaluated for concordance between the two test methods using standard statistical methods.

#### 7.0 Documentation

#### 7.1 Data Reporting Forms and Tracking Log Sheets

Any required forms regarding study data or material inventory tracking (for specimens or assay reagents) will be completed in ink (black ball-point pen is preferred). Entries made with pencil are not allowed. When completing forms, do not leave blanks. If an item is missing, complete the entry with 'ND' for 'not done' or 'NA' for 'not available/applicable,' as appropriate.

All changes or corrections to any original document must be made in ink and initialed and dated by the person making the change. Incorrect data should be indicated by lining through the entry with a single line. Do not erase or use correction fluid ("White-Out" or "Liquid Paper") or eradicate the entry in any other way. The correct value should be written next to the item in question and circled. Each page with corrections must be initialed and dated by the technician performing the assay.

Assigned EDP Biotech Corp. personnel responsible for entries made to any study form will provide a signature and date on each form sheet upon completion. The Clinical Investigators (or designee) must review all study forms related to data reporting or material tracking. The Clinical Investigators are ultimately responsible for the integrity of the data recorded or submitted on the data reporting form.

#### 7.2 Subject Questionnaire

Each subject will be asked to complete forms providing information about exhibited symptoms consistent with COVID-19 infection (Appendix 3 & 4), and forms regarding the comprehension of the test (Appendix 5).

#### 7.3 Instrument-Generated Printouts

Any instrument-generated data printed results for each assay run (including all valid and invalid runs) must be reviewed for accuracy and signed and dated by the Principal Investigator (or designee) and then included in the study regulatory binder.

#### 7.4 Specific Tracking Log Sheets

All test materials and controls used during the study will be recorded to indicate lot and expiration date.

# 8.0 IRB Requirements

#### 8.1 Informed Consent

The study described in this protocol presents a nonsignificant risk of harm to the human subjects, as standard procedures are used for the AN swab and nasopharyngeal swab specimen collections. EDP Biotech Corp. has determined Informed Consent (IC) is appropriate from individuals to provide specimens for the research study. A proposed Informed Consent Form is presented as Appendix 8.

For this study:

- a) This investigation meets the IDE exemption criteria at  $21\ \text{CFR}\ 812.2\text{(c)}$  (3).
- b) The specimens will not be individually identifiable, i.e., the identity of the subject is not known after specimen collection based on the unique identifier and may not readily be ascertained by EDP Biotech Corp. employees or any other individuals associated with the investigation after the unique SID is assigned. In this manner, the specimens will be coded but will be individually identifiable by the clinical investigator(s) so that study participants can be given the results of the nasopharyngeal swab sample analysis for COVID-19 RNA (positive or negative).
- c) The samples are provided to the laboratory staff and investigator(s) in a de-identified state, i.e., without the name of the subject, thus preventing the unintentional release or dissemination of personal information or testing results.
- d) The study will be reviewed by an IRB in accordance with 21 CFR Part 56.

#### 8.2 IRB Approval

This study will be initiated only after IRB Approval of the study has been granted. A copy of the IRB approval document will be maintained by the Clinical Investigators in a study binder.

# 9.0 Risk Analysis

This is a non-significant risk device study. The study presents no potential for serious risk to the health, safety, or welfare of any human subject as it uses only commonly employed techniques for the AN swab and nasopharyngeal swab specimens. There will be subject recruitment at the EDP Biotech Corp.

investigative site using public posting, e-mail correspondence, and referrals. Study results will be used to demonstrate that the Rapid SARS-CoV-2 Antigen Test technique is suitable for home use without a prescription.

# 10.0 Study Master File (SMF)

The Clinical Investigator (CI) or Designee(s) will collect and review copies of the required essential documents (ED) listed below in the form of a Study Master File (SMF). EDP Biotech Corp. will maintain the SMF and copies of the required EDs; the Investigator Site File (ISF) will contain original documents. MP Biomedicals is the sponsor of the study and will maintain copies of the required EDs as well.

#### **10.1 Required Essential Documents**

A binder(s), which for purposes of this clinical study will be defined as the investigator site file (ISF), will be maintained at the trial site and serves as the central source for ED maintenance at the site.

The following documents represent a complete site essential document packet and are to be maintained in the ISF:

- Clinical Investigator's (CI) Curriculum Vitae (CV) or Resume.
- CI Human Subject Protection Training documentation.
- Institutional Review Board (IRB)-Approved Protocol and Protocol Amendments.
- Protocol/Protocol Amendment(s) Signature Pages.
- IRB Compliance Documentation.
- Signed informed consent forms.
- Laboratory Certifications, e.g. CLIA.

# 11.0 Monitoring

The sponsor of this study shall be responsible for ensuring adequate monitoring for the study occurs. The Clinical Investigators will grant the sponsor or designee access to the testing site and all applicable study information. Access will be granted to review all study documents and all Regulatory documentation (site binders containing completed ICFs and IRB approval). Monitoring of the study will be conducted on a periodic basis throughout the evaluation. Closeout monitoring of the study will be conducted. Reports of the monitoring will be prepared. Any deficiencies observed during the monitoring will be discussed with the Clinical Investigator for remediation. Monitoring may be conducted remotely.

# 12.0 Investigational Study Site Compliance

#### 12.1 Investigator Responsibility

The Clinical Investigator (CI) is expected to ensure that the methods and study design outlined in this protocol are followed. No changes to protocol methods or study design can be made without the written consent of the sponsor. It is the responsibility of the sponsor and the CIs to ensure subject confidentiality and IRB approval for the study.

### 12.2 Site Monitoring and Inspection

The sponsor will maintain close liaison with the study Investigators to answer any questions that may arise and to ensure that the study is being conducted according to this protocol. The study site will permit the sponsor and/or its designee to visit the site at reasonable times to audit or inspect the study records and materials. Sponsor personnel will audit the progress and compliance of the study and at the end of the study for closeout.

#### 12.3 Record Retention

Study records will be maintained by the Clinical Investigators and Study Sponsor per EDP Biotech Corp. SOPs. Copies of all data generated from the study, all data reporting forms, and records of reagent disposition are to be maintained for a period of 5 years following the date on which the entire clinical investigation is terminated or discontinued.

# 13.0 Biological Safety

#### 13.1 Toxicity and Complications

Not applicable.

#### 13.2 Sample Handling

All volunteer specimens and materials with which the study personnel come into contact should be handled as if capable of transmitting infection, and dispensed of with precautions in accordance with Federal, State, and Local regulations.

#### 14.0 Modifications to the Protocol

#### 14.1 Protocol Amendments

Neither the Clinical Investigators nor study laboratory personnel will modify this protocol without contacting the Study Sponsor.

#### 14.2 Study Termination

For any reasonable cause, the Study Sponsor may terminate the study, provided a written notice is submitted at least 30 days in advance of the intended termination. The IRB will be notified if the study is terminated.

# 15.0 Abbreviations

The abbreviations that are given below apply:

# 15.1 Abbreviations

$^{\circ}\mathrm{C}$	Celsius (Centigrade)
μg	Microgram
μl	Microliter
AE	Adverse Event
AMR	Analytical Measurement Range
AN	Anterior nasal (nares)
CFR	Code of Federal Regulations
dL	One-tenth of a liter
d	Day
FDA	Food and Drug Administration
hrs	Hours
IC	Informed Consent
ID	Identification or identification number
IDE	Investigational Device Exemption
IFU	Instructions for use
IRB	Institutional Review Board
IUO	Investigational use only
LIS	Laboratory information system
mL	Milliliter
N	Number
NA	Not applicable or not available
ND	Not done
Ng	Nanogram
OTC	Over the counter
PI	Principal Investigator
QC	Quality Control
RT	Room temperature (ambient)
RUO	Research Use Only
SAE	Serious Adverse Event
SOC	Standard of care
SOP	Standard Operating Procedure
wks	Weeks

Over the counter Rapid Antigen Test for detection of SARS-CoV-2 virus: Clinical Evaluation Statistical Analysis Plan

December 1, 2021

Protocol Number: EDP-SOP-TNC-014 Sponsored by: MP Biomedicals, LLC [name]

Statistical Analysis Plan for EDP-SOP-TNC-014

Data Evaluation and Accessibility

A report tabulating and analyzing the data will be prepared by the Clinical Investigator including tables of the results and a description of any deviations from the protocol.

Acceptability of Data for Analysis

Valid individual specimen results generated in invalid runs are not acceptable for inclusion in final data analysis. Samples tested in invalid runs must be re-tested if the remaining specimen volume is available. Only valid results from specimens in valid runs will be included in the final data analysis.

Exclusion of Data from Analysis

Data from invalid runs results will be excluded. All excluded results will be documented with rationale for exclusion and a summary of these cases will be provided.

Data Entry and Corrections to Study Documents

All entries must be legible and made in indelible ink (preferably black); do not use pencil. Strike incorrect entries with a single line (do not obliterate or put "white-out" on the original entry). Then enter the correct information next to the original entry, initial, and date the correction.

Assay Run Data

Any Printouts corresponding to assay runs will be maintained and a copy placed in a study binder. A record will be maintained regarding assay reagents and calibrators by lot number and expiration date.

Discordant Results

If any discordant results are generated during the clinical study, further testing using a second high-sensitivity EUA PCR method, CDC's Influenza SARS-CoV-2 (Flu SC2) Multiplex Assay performed by Premier Laboratories, will be performed with specimens yielding discordant results obtained with the initial PCR methodology. If the NP swab sample has been retained and stored properly, and there is sufficient sample available, the same sample will be run on the second PCR assay. Both the AN specimen and the nasopharyngeal swab specimen can be repeat tested if possible. The results from the discrepant analysis will be reported as a footnote in the performance table. The discordancy will not be used to alter the performance data.

Acceptance Criteria for Method Comparison

The study sponsor or designee will ensure that all specimens are analyzed appropriately, and results are accurately transcribed to an excel spreadsheet for analysis. Qualitative results from the Antigen Test and quantitative results from the PCR Test may be evaluated for concordance between the two test methods using standard statistical methods.

Sensitivity and Specificity Analyses

Analysis will be conducted according to the Clinical and Laboratory Standards Institute EP05-A3 Evaluation of Precision of Quantitative Measurement Procedures: Approved Guideline – Third Edition. Formulas used to calculate sensitivity (PPA) and specificity (NPA) are as follows:

- Positive Percent Agreement (PPA) = True Positive/(True Positive + False Negative)
- Negative Percent Agreement (NPA) = True Negative/(False Positive + True Negative)

95% confidence intervals for sensitivity and specificity are as follows:

- 95% Confidence Interval for PPA:
 - $\circ Q_{1PPA} = 2 \times True \ Positive + 3.84$
 - $\circ \quad Q_{2PPA} = 1.96 \times \sqrt{3.84 + 4 \frac{\text{True Positive} \times \text{False Negative}}{\text{True Positive} + \text{False Negative}}}$
 - \circ $Q_{3PPA} = 2 \times (True Positive + False Negative) + 7.68$

• Lower bound =
$$100 \times \frac{Q_{1PPA} - Q_{2PPA}}{Q_{1PPA} - Q_{2PPA}}$$

- Upper bound = $100 \times \frac{Q_{3PPA}}{Q_{1PPA} + Q_{2PPA}}$
- 95% Confidence Interval for NPA:
 - $\circ \quad Q_{1NPA} = 2 \times TN + 3.84$

$$\circ \quad Q_{2NPA} = 1.96 \times \sqrt{3.84 + 4 \frac{True \, Negative \times False \, Positive}{True \, Negative + False \, Positive}}$$

 \circ $Q_{3NPA} = 2 \times (True Negative + False Positive) + 7.68$

• Lower bound =
$$100 \times \frac{Q_{1NPA} - Q_{2NPA}}{Q_{1NPA}}$$

• Upper bound =
$$100 \times \frac{Q_{1NPA} + Q_{2NPA}}{Q_{3NPA}}$$

- Analysis for sensitivity, specificity, and 95% confidence intervals based on days post-symptom onset will be conducted as follows:
 - Subjects considered symptomatic according to the November 9, 2021 FDA EUA guidance will be separated into the following categories based on the number of days after symptom onset that they report when they present for testing:
 - 0-1
 - 0-2
 - 0-3
 - 0-4
 - 0-5
 - 0-6
 - 0-7
 - 0-14
 - 0-15+
 - Reported exposure, not symptomatic

[name] Ph: [contact] Toll Free: [name] [contact] www.EDPbiotech.com

- The sensitivity, specificity, and 95% confidence intervals for each category of days post-symptom onset will be calculated based on the cumulative number of subjects who fit into that category.
- The subjects considered symptomatic will also be separated into the following categories in order to calculate the sensitivity and its 95% confidence interval based on non-cumulative reported days post-symptom onset:
 - 0
 - 1
 - 2
 - 3
 - 4
 - **5**
 - 6
 - 7
 - 8 to 14
- Analysis for sensitivity, specificity, and 95% confidence intervals based on presence of symptoms or reported exposure and based on absence of symptoms or reported exposure.
 - Subjects considered symptomatic according to the November 9, 2021 FDA EUA guidance will be collectively analyzed for sensitivity and specificity using the above formulas.
 - Subjects considered asymptomatic according to the November 9, 2021 FDA EUA guidance will be collectively analyzed for sensitivity and specificity using the above formulas.
- Analysis will also be conducted for all subjects (total sample size of 188), regardless of categorization, using the same above formulas for sensitivity, specificity, and the 95% confidence intervals.
- Overall positivity rate for the subject population will be calculated based on age group and reported gender.
 - Age groups will be separated based on the November 9, 2021 FDA EUA guidance into the following categories:
 - 2 to 13 years of age
 - 14 to 24 years of age
 - 25 to 64 years of age
 - 65+ years of age
 - Gender will be separated into male and female. No consideration will be given to gender identity or categories other than male and female.
 - Positivity rate will be calculated based on the results of the comparator method(s) used to gauge the efficacy of the candidate device.
 - This will be calculated for each of the above age groups, as well as for the subject population overall. The total number of subjects in each age group who test positive on the candidate device will also be calculated.
 - The total number of males and females in the study population will be calculated, and further separated by the above age groups.
- Analysis for sensitivity and 95% confidence intervals based on comparator cycle threshold (Ct) value will be conducted as follows:

- Cycle threshold values will be separated into the below categories. These are based on the number of PCR cycles taken by the comparator method to detect enough viral material to report a positive result. The higher the Ct value is, the lower the viral load of the sample:
 - 10 to 14
 - 15 to 19
 - 20 to 24
 - 25 to 29
 - 30 to 34
 - 35+
- Sensitivity and its 95% confidence interval will be calculated for each category.
- The mean, median, and minimum and maximum Ct values will be calculated for each category of subjects based on reported days post-symptom onset.
- Sensitivity and its 95% confidence interval for positive samples determined to have a low viral load (samples with Ct values greater than or equal to 32) will be calculated using the formulas above for each of the following categories:
 - 10% of the 12 low-positive samples
 - 15% of the 12 low-positive samples
 - o 20% of the 12 low-positive samples

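### Are three of the four confidence-bound formulas for PPA and NPA in the SAP wrong?

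*SAP*

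**What the plan says.** The relevant part of the SAP is the section on sensitivity and specificity analyses, introduced by "95% confidence intervals for sensitivity and specificity are as follows". For PPA it defines three terms:

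- "Q_{1PPA} = 2 \times True \ Positive + 3.84"
- "Q_{2PPA} = 1.96 \times \sqrt{3.84 + 4 \frac{\text{True Positive} \times \text{False Negative}}{\text{True Positive} + \text{False Negative"
- "Q_{3PPA} = 2 \times (True Positive + False Negative) + 7.68"

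The NPA terms are the same, with true negatives and false positives in place of true positives and false negatives. In the machine-read text the four bounds then appear as follows:

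- PPA lower: "100 \times \frac{Q_{1PPA} - Q_{2PPA}}{Q_{1PPA} - Q_{2PPA", i.e. (Q1 − Q2)/(Q1 − Q2).
- PPA upper: "Upper bound = $100 \times \frac{Q_{3PPA}}{Q_{1PPA} + Q_{2PPA", i.e. Q3/(Q1 + Q2).
- NPA lower: "100 \times \frac{Q_{1NPA} - Q_{2NPA}}{Q_{1NPA", i.e. (Q1 − Q2)/Q1.
- NPA upper: "100 \times \frac{Q_{1NPA} + Q_{2NPA}}{Q_{3NPA", i.e. (Q1 + Q2)/Q3.

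The SAP gives no worked example and no numerical bound. Protocol section 2.2 sets the acceptance criteria at PPA of at least 80% and NPA of at least 98%, and mentions no confidence limit.

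**The concern.** Only the last of the four is a usable bound. A quantity divided by itself is 1, so the PPA lower bound would be 100% whatever the data. The PPA upper bound is upside down and would exceed 100% as soon as there is a false negative. The NPA lower bound divides by Q1, which is smaller than Q3, so it would come out too high.

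These formulas are the SAP's only specification of the interval. It refers back to them for the symptomatic, asymptomatic, all-subject and low-viral-load analyses, and gives no other formula for the day-of-onset and Ct bands. Results go into an Excel sheet, so the formulas might be typed in by hand. An impossible PPA interval would be noticed. A favourable but plausible NPA lower bound might not.

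**Working it through.** **Inputs.** Q1, Q2 and Q3 come from the SAP. The minimum of 30 PCR positives and 30 PCR negatives is in Protocol section 4.4. The total of 188 is in the SAP. The count of 158 negatives is an assumption (188 − 30), used only to show size.

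**What the Q terms define.** For x agreements out of n, the Wilson 95% limits are

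(2x + z² ± z√(z² + 4x(n − x)/n)) / (2n + 2z²), with z = 1.96 and z² = 3.84.

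So Q1 = 2x + z², Q2 is the square-root term, and Q3 = 2n + 2 × 3.84 = 2n + 7.68. These match the SAP's definitions term by term, and Q3's role is the denominator. With Q3 under all four bounds, the SAP's terms agree with a separately computed Wilson interval to within 0.003 percentage points at n = 30, 60, 158 and 188.

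**PPA at 24/30.**

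- Q1 = 2 × 24 + 3.84 = 51.84
- Q2 = 1.96 × √(3.84 + 4 × 24 × 6/30) = 1.96 × √23.04 = 1.96 × 4.8 = 9.408
- Q3 = 2 × 30 + 7.68 = 67.68
- With Q3 as denominator: (51.84 − 9.408)/67.68 = 62.7% and (51.84 + 9.408)/67.68 = 90.5%
- As the text reads: 42.432/42.432 = 100% and 67.68/61.248 = 110.5%

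**NPA lower bound.**

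| Count | Q1 | Q2 | Q3 | As the text reads, (Q1 − Q2)/Q1 | (Q1 − Q2)/Q3 |
|---|---|---|---|---|---|
| 30/30 | 63.84 | 3.841 | 67.68 | 94.0% | 88.7% |
| 29/30 | 61.84 | 5.441 | 67.68 | 91.2% | 83.3% |
| 155/158 | 313.84 | 7.744 | 323.68 | 97.5% | 94.6% |
| 158/158 | 319.84 | 3.841 | 323.68 | 98.8% | 97.6% |

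The literal reading is therefore too high by about 5 to 8 points at n = 30, and by about 1 to 3 points at n = 158 near the 98% criterion.

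**Where the malformed bounds come from.** Suppose the page shows both PPA bounds as stacked fractions over Q3. Read down the page, the terms are:

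1. Q1 − Q2 (lower, numerator)
2. Q3 (lower, denominator)
3. Q1 + Q2 (upper, numerator)
4. Q3 (upper, denominator)

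The upper bound in the machine-read text is term 2 over term 3. The lower bound, having lost its denominator to the next line, shows term 1 twice. The NPA lower bound differs from the correct form by one digit in a small subscript, Q1 for Q3. The NPA upper bound, which has no further bound below it, reads correctly. The same reading also put stray mathematical symbols into the Protocol's table of contents, so faults of this kind occur elsewhere in the text.

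**The case for a change.** The strongest reply is that the text must be taken as it stands. The SAP names no interval method, and the guideline it cites is, by its title, about precision of quantitative measurements, so a programmer has only these formulas to follow. The nested fraction in Q2 was read without fault, which shows the reading does not always fail. The displaced-denominator explanation fits the PPA pair closely but the NPA lower bound less neatly: that fraction has an intact numerator and a well-formed denominator that is simply the wrong term. At 153/158 the literal lower bound, 96.95%, would even lie above the estimate of 96.84%.

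The arithmetic in this reply stands, and so does the point that the text alone cannot prove a reading fault. It does not establish an error by the authors. Someone who misunderstood the method, or copied a block of formulas, would be expected to repeat one mistake for both PPA and NPA. Here three bounds fail in three different ways beside correct definitions of all the Q terms and one correct bound. An author is also unlikely to write a fraction with the same numerator and denominator. A misread subscript is enough to explain the NPA lower bound.

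**Conclusion.** The concern does not hold as an error in the plan. The SAP's terms specify the Wilson score interval, its intact NPA upper bound shows Q3 as the denominator, and the three malformed bounds are best explained as stacked fractions misread from the PDF. This is an inference from the pattern; the typeset page would settle it. If the page shows Q3 under every bound, nothing needs to change.

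If it did not, the reported intervals would be affected by the amounts shown above, with the n = 158 figures resting on an assumed count. The trial's pass or fail would still be the same, because the criteria in Protocol section 2.2 name PPA and NPA values without a confidence bound. What is left is a check of the page, which alters nothing the trial does or concludes.

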#### 2.2 Study Objectives

The objective of the study is to evaluate the feasibility of using Rapid SARS-CoV-2 Antigen Test detection of SARS-CoV-2 virus in OTC home use. The presence of SARS-CoV-2 virus will be confirmed by PCR methodology. Testing will be performed with EUA PCR tests. The acceptance criteria for this study is Positive Percent Agreement (PPA) greater than or equal to eighty percent and Negative Percent Agreement (NPA) greater than or equal to ninety-eight percent).

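### The low-viral-load (Ct ≥ 32) sensitivity is defined on 10%, 15% and 20% of 12 specimens, which is 1 to 3 specimens with no rule for choosing them

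*SAP*

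**What the plan says.** The last item under Sensitivity and Specificity Analyses in the SAP asks for sensitivity and its interval in a group it describes thus: "low viral load (samples with Ct values greater than or equal to 32) will be calculated using the formulas above for each of the following". Three subsets are then listed. The first is "10% of the 12 low-positive samples", the second is "15% of the 12 low-positive samples" and the third is "20% of the 12 low-positive samples".

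The formulas referred to are those at the start of the same SAP section: PPA as true positives over true positives plus false negatives, and a 95% interval built from Q1, Q2 and Q3.

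Three other parts of the plan bear on the point:

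- **Ct bands.** Just before the low-viral-load item, the SAP sets bands that include 30 to 34 and 35+, and states: "Sensitivity and its 95% confidence interval will be calculated for each category".
- **Overall analysis.** "Analysis will also be conducted for all subjects (total sample size of 188), regardless of categorization".
- **Acceptance criteria (Protocol 2.2).** "The acceptance criteria for this study is Positive Percent Agreement (PPA) greater than or equal to eighty percent", with NPA at 98% or more. Ct plays no part in either.

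Protocol 4.4 sets a minimum of 30 PCR positives but no quota for low positives. The Protocol mentions neither low positives nor a Ct threshold of 32.

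**The concern.** PPA is a ratio of whole-specimen counts, and none of the three percentages of 12 is a whole number. The SAP does not say how to round, which specimens to take (at random, by Ct or in order of enrolment), whether the categories are nested, or where the 12 comes from. Two analysts could follow the text and report different sensitivities from the same data.

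What is at stake is the one analysis devoted to the specimens an antigen test is most likely to miss; the SAP itself notes that a higher Ct means a lower viral load. Protocol 4.0 says the data may go into a regulatory filing, where a figure resting on an unspecified choice of 1 to 3 specimens would be hard to defend. Sensitivity on the whole Ct ≥ 32 group is never requested.

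**Working it through.** **Inputs.** From the SAP: 12 low positives; shares of 10%, 15% and 20%; total sample size 188; the PPA formula; and the interval components. The number of the 12 that the antigen test detects is not in the documents, so I assume 3, 6 or 9 to show a range.

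The SAP gives the 12 as a bare count. No input in either document lets it be derived, so there is no planned figure to reproduce.

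**Step 1: category sizes.** 0.10 × 12 = 1.2; 0.15 × 12 = 1.8; 0.20 × 12 = 2.4.

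| Rounding | 10% | 15% | 20% |
|---|---|---|---|
| Down | 1 | 1 | 2 |
| Nearest | 1 | 2 | 2 |
| Up | 2 | 2 | 3 |

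Under each of these conventions, two of the three categories have the same size.

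**Step 2: what such a category can show.** The components are those of the Wilson score interval: Q1 = 2·TP + 3.84; Q2 = 1.96·√(3.84 + 4·TP·FN/(TP + FN)); Q3 = 2·(TP + FN) + 7.68. The limits are (Q1 − Q2)/Q3 and (Q1 + Q2)/Q3. I use this standard form because the PPA bounds are not legible in the text I had; nothing here turns on that.

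With every specimen detected, FN = 0 and Q2 = 1.96·√3.84 = 3.841. The lower limits are:

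- 1/1: (5.84 − 3.841)/9.68 = 20.7%
- 2/2: (7.84 − 3.841)/11.68 = 34.2%
- 3/3: (9.84 − 3.841)/13.68 = 43.9%

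**Step 3: dependence on which specimens are picked.** There are 12, 66 and 220 possible subsets of size 1, 2 and 3. If k of the 12 are detected, a random subset of size n gives 0% or 100% with probability [C(k,n) + C(12−k,n)]/C(12,n).

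| Detected (assumed) | n = 1 | n = 2 | n = 3 |
|---|---|---|---|
| 3 of 12 | 100% | (3 + 36)/66 = 59% | (1 + 84)/220 = 39% |
| 6 of 12 | 100% | (15 + 15)/66 = 45% | (20 + 20)/220 = 18% |
| 9 of 12 | 100% | (36 + 3)/66 = 59% | (84 + 1)/220 = 39% |

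In every row, the choice of specimens alone can move the reported sensitivity from 0% to 100%.

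**Step 4: using all 12.** Wilson intervals are 8.9% to 53.2% (3/12), 25.4% to 74.6% (6/12) and 46.8% to 91.1% (9/12). These are wide, but the data determine them.

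**Step 5: the alternative reading.** Suppose the percentages were meant as the low-positive share of all PCR positives. Then 12 would be 10%, 15% or 20% of 12/0.10 = 120, 12/0.15 = 80 or 12/0.20 = 60 positives, which is 64%, 43% or 32% of 188. One dataset with 12 low positives has only one observed share, so three results would need reweighting or subsampling. The SAP specifies neither.

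**The case against.** The best defence has three parts.

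**Scope.** No decision rule uses these lines. The acceptance criteria ignore Ct, the overall analysis covers all subjects, and the 30 to 34 and 35+ bands report high-Ct specimens with intervals. A reader would discount a result on 1 to 3 specimens at once. This stands as a limit on severity. It does not make the lines harmless: the 30 to 34 band straddles 32, so adding the two bands mixes in Ct 30 and 31 specimens and does not recover the Ct ≥ 32 group.

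**Intent.** The authors may have meant PPA with low positives making up 10%, 15% or 20% of all positives, and three such figures can be had from one dataset by reweighting. That is possible, and the documents do not settle it. But the text takes percentages of the 12 and restricts the analysis to Ct ≥ 32, so on that reading the wording is still wrong and the method is still missing.

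**Assumptions.** The probabilities in step 3 rest on an assumed detection count. That is fair, but the category sizes and the lower bounds for perfect detection make the point without it.

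A narrower point also stands: equal category sizes follow from rounding all three the same way. With no rule stated, sizes of 1, 2 and 3 could also be chosen.

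**Conclusion.** The concern holds, with high confidence, and should be fixed. As worded, the Ct ≥ 32 analysis cannot be carried out without inventing a rounding rule and a selection rule. Whatever is invented, each category holds 1 to 3 specimens and its lower bound cannot exceed 43.9%. PPA on all Ct ≥ 32 positives is never reported.

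The category sizes and these bounds need no assumption beyond the SAP's own 12 and the standard form of its interval. The chance of an all-or-nothing result (18% to 100%, depending on subset size) assumes 3, 6 or 9 of 12 detected and random selection. The effect is confined to this table; overall PPA, NPA and their acceptance criteria are untouched.

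**What to change.** Replace the three lines with: *PPA and its 95% score interval will be calculated for every PCR positive with Ct ≥ 32, whatever the count.* Delete the fixed 12.

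Ask the sponsor what the percentages refer to. Only if they were meant as the low-positive share of all PCR positives, say so and add PPA_w = w × PPA(Ct ≥ 32) + (1 − w) × PPA(Ct < 32) at w = 10%, 15% and 20%. Build the interval from the Wilson limits of each stratum. The lower limit is the estimate minus the square root of the summed squared weighted distances to the stratum lower limits; the upper limit is formed likewise. With an assumed 6/12 low and 45/48 other positives detected, this gives 89.4% (79.5 to 93.8), 87.2% (77.5 to 92.3) and 85.0% (75.2 to 90.9). The interval keeps its width when a stratum is at 0% or 100%: 0/12 and 48/48 at w = 10% gives 90.0% (83.3 to 92.4).

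Optionally, make 32 a boundary of the Ct bands and use half-open bands, so that the bands and the low-viral-load group agree.

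The cost is a few lines of SAP text and some spreadsheet cells, with no new data. The drawback is a wide interval, which is what about 12 specimens can support.
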